7.7. Months 6, 12, 18 and 24 – Follow-up

Patients will return 6, 12, 18, and 24 months (+/-30 days) post cryoablation procedure. In the event of multiple cryoablation procedure dates, the most recent procedure date will serve as the reference for determining the follow up visit window.

The following assessments will be completed:

- Karnofsky Performance Scale;
- Chest CT scan \pm contrast (contrast is preferred);
- Safety assessment;
- Assessment of metastatic lung disease progression beyond the index tumor and feasibility of treatment;
- Assessment of local tumor recurrence at the index tumor, including additional treatment and feasibility of treatment;
- Assessment of any systemic cancer treatment(s);
- Assessment of any local therapy for the index tumor(s).

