8.7. Response Determination

The month 1 post-ablation CT examination will be used as the reference for determining index ablation zone response at each follow up interval after cryoablation. Sequential follow up intervals will be used to determine local failure.

In the unforeseen circumstance where the patient is unable to complete imaging according to the month 1 follow up visit, the month 3 imaging study may serve as the reference for determining index tumor response at each follow up interval after cryoablation. Every effort should be made to comply with the month 1 imaging requirement.

Efficacy at 12 months post cryoablation will be based on local tumor control that will be separately assessed for each index tumor according to criteria below. Each ablation zone will be evaluated at each time point by measuring its 3 axes (longest diameter and the two perpendicular diameters). For each ablation zone individually, the sum of these three measures will be compared to the 1 month baseline for tumor response and the previous follow up interval imaging study for local failure.

Each ablation zone measurement assessment, along with the overall clinical evaluation of the patient, will be evaluated by an independent imaging panel to assess the final response determinations. This final review can be used in the analysis in the event of 'indeterminate' imaging measurement assessments.

Local Tumor Control will be defined as the absence of local failure.

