8.7.2 Partial Response

Partial response will be defined as $\geq 30\%$ decrease in the 1 month baseline sum of the three axes of measurements (longest diameter and the two perpendicular diameters).

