8.7.4 Local Failure

Local failure will be defined as $\geq 20\%$ increase in the sum of the three axes of measurements (longest diameter plus the two perpendicular diameters) when compared with the nadir of this 3 axes measurement.

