For the formal primary endpoint hypothesis test, patients with missing 12-month tumor evaluations will be imputed using multiple imputation (SAS PROC MI using FCS logistic regression and including tumor status at prior visits), except in the following case where previous visit evidence can be used to impute 12-month status:

- Subjects with local tumor failure at 6-months will be considered a local tumor failure at 12-months post-index procedure.

Additional sensitivity analyses to be conducted:

- Worst case: all missing data are imputed to be failures
- Best case: all missing data are imputed to be successes
- Complete case: all missing data are treated as missing and not imputed

Subset Analyses

Analysis will be done on outcomes for subgroups including, but not limited to, gender and lesion size. Additional non-protocol defined subgroups include: number of needles used, number of lesions, primary cancer diagnosis, and lesion location.

Poolability Analyses

A poolability analysis among investigational centers and geographies (US/OUS) will be performed for the primary efficacy endpoint. This analysis will be performed on the ITT population.

Poolability of Sites

Combining of Small Sites

Sites contributing less than 5 subjects to the as treated analysis set will be considered “small sites” and ordered by the date of first enrollment in the as treated analysis set. Starting with the first “small site”, a pseudo-site will be created by adding subjects from successive “small sites”. If the number of subjects reaches or exceeds the size of the median enrollment of the “large sites”, then a second pseudo-site will be created. Additional pseudo-sites, if needed, would be created in the same manner.

Primary Endpoint by Site

Among sites and pseudo-sites, the proportions of subjects who achieve local tumor control at 12 months will be compared using logistic regression. If the resulting p-value is ≤ 0.05 , further exploratory analysis will attempt to identify covariates (baseline characteristics) that may explain differences among the sites. Otherwise, the data will be considered to be poolable across study sites.

Poolability of Geographies

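### The primary-endpoint imputation names only prior tumor status, which barely varies among the tumors left to impute; measured growth should be added to the model

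*SAP*

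**What the plan says.** The SAP section Handling of Missing Data imputes missing month-12 evaluations for the formal test by multiple imputation (MI): "SAS PROC MI using FCS logistic regression and including tumor status at prior visits". It names no other predictor and does not define tumor status. One deterministic rule comes first: "Subjects with local tumor failure at 6-months will be considered a local tumor failure at 12-months post-index procedure". Worst-case, best-case and complete-case analyses follow as sensitivity analyses.

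Protocol 8.7 makes the endpoint binary: "Local Tumor Control will be defined as the absence of local failure". Local failure (8.7.4) is an increase of 20% or more in the three-axis sum "when compared with the nadir of this 3 axes measurement". Sections 8.7.1 to 8.7.3 also grade complete response, partial response and stable disease. Size is on record throughout: "Each ablation zone will be evaluated at each time point by measuring its 3 axes". Scans continue at months 18 and 24 (7.7), but the imputation refers to prior visits only. Under 7.8, a patient whose index tumor receives a different local treatment must be withdrawn, and neither document sets that tumor's month-12 status.

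**The concern.** An imputation model corrects for selective loss only if its predictors separate high-risk from low-risk losses. Under the binary reading, once month-6 failures are removed, the one named predictor takes a single value in every remaining tumor that has a month-6 scan. (Tumors with a month-3 failure and no month-6 scan differ, but should be few.) The model then draws at the month-12 control rate of tumors that were controlled earlier and stayed under observation. A tumor 15% above its nadir at month 6 whose patient then leaves is imputed like one that has vanished.

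This matters because the single-arm test compares the imputed rate with a fixed 84% goal. If regrowing tumors are lost more often, the error favors meeting the goal.

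**Working it through.** **Design figures.** Exact binomial, N = 203, reject at 181 or more: P(R ≥ 181 | 0.84) = 0.0239 and P(R ≥ 181 | 0.91) = 0.850, as stated. 203/0.90 = 225.6, so 226. At N = 226 the same test needs 201 (88.9%; tail probability 0.0227 at 84%).

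**Would graded status help?** Take a month-1 sum of 100 and a nadir of 50. A month-6 sum of 57.5 is 15% over nadir, yet 42.5% below month 1, so it is a partial response. A tumor shrinking steadily to 57.5 gets the same grade. The grades mostly measure change from month 1 and say little about growth over nadir.

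**Size of the bias (large-sample arithmetic, tumors independent).** None of these inputs is in the documents; all are assumed:
- 10% of tumors are regrowing, with month-6 growth N(15%, 7%). The rest are N(0, 8%), floored at 0.
- Growth of 20% or more at month 6 is failure and is carried forward.
- Of tumors not failed at month 6, 80% of regrowers and 2% of the others fail by month 12.

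| Month-6 growth | Regrowers (share of all) | Others (share of all) |
|---|---|---|
| under 10% | 0.0238 | 0.8049 |
| 10-20% | 0.0525 | 0.0895 |
| 20% or more | 0.0238 | 0.0056 |

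True control = 0.20 × (0.0238 + 0.0525) + 0.98 × (0.8049 + 0.0895) = 0.892.

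Bias of status-only MI = (share left to impute) × (rate at which they are imputed − their true rate).

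Worked case, 35% missing at 10-20% growth and 7% otherwise:
- Left to impute: 0.35 × 0.1420 + 0.07 × 0.8287 = 0.1077.
- True control among them: 0.0899/0.1077 = 0.835.
- Control among observed tumors controlled at month 6: (0.8918 − 0.0899)/(0.9707 − 0.1077) = 0.929.
- Bias: 0.1077 × (0.9292 − 0.8349) = +1.0 point.

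| Missing: 10-20% growth v rest | Missing overall | Imputed at | True rate | Bias of MI | Bias of complete case |
|---|---|---|---|---|---|
| 35% v 7% | 11.0% | 92.9% | 83.5% | +1.0 | +0.9 |
| 20% v 9% | 10.6% | 92.3% | 88.4% | +0.4 | +0.3 |
| 10% v 10% | 10.0% | 91.9% | 91.9% | 0 | 0 |
| 35% v 7%, month-6 failures also 35% missing | 11.8% | 92.9% | 83.5% | +1.0 | +1.7 |

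Adding measured growth to the model brought the MI bias to within 0.03 points of zero in the growth scenarios.

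**False-pass risk.** A separate simulation fixed true control at 84%: 226 independent tumors, 3,000 trials, 20 imputations, Rubin's rules and a logit-Wald bound. It assumed that 8% fail by month 6, that the log-odds of later failure rise 1.2 per SD of growth, and that the log-odds of a missing month 12 rise 1.0 per SD.

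| Missing | Status-only: rate, P(pass) | Growth added: rate, P(pass) |
|---|---|---|
| 10% | 84.4%, 2.6% | 84.0%, 1.8% |
| 20% | 84.8%, 4.4% | 83.9%, 1.9% |
| 30% | 85.2%, 5.8% | 83.9%, 2.2% |

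Monte Carlo error near 2.5% is √(0.025 × 0.975/3000) ≈ 0.3 points, so 2.6% does not differ from the nominal 2.5%. With missingness unrelated to growth, both models were close to unbiased (83.9 to 84.0%) and passed in 1.5 to 2.2% of trials.

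**Sensitivity analyses.** With 185 of 203 controlled (91.1%) and 23 missing, worst case is 185/226 = 81.9% and best case is 208/226 = 92.0%. The pair straddles the goal, and nothing planned lies between them except complete case.

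**The case against.** The strongest reply is that the SAP does not exclude growth data. Its wording gives prior status as something the model includes, not as the whole list, and status could mean the graded response. That stands: a reader might infer that measured size is barred from the model, and the text does not say so. But a plan for a decisive test should name its predictors, and the grades would close only part of the gap.

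The second reply is that the mechanism is assumed. Nothing in the documents says that growth below 20% leads to other local treatment. Protocol 7.8 permits repeat cryoablation within the study, and the cited series report one-year survival of 91% and 89.4%, so death may account for much of the missingness. This also stands, and it is why the size is given as a range that starts at zero.

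Third, a reader might infer that this MI does no better than complete case. That holds only if documented failures leave no more often than stable tumors. When they also drop out, the carry-forward rule captures them and MI is clearly better (+1.0 against +1.7).

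Finally, the planned worst-case and best-case analyses do bound the effect. They do not decide the primary test.

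**Conclusion.** The point holds as a specification gap with a cheap and better alternative. The only named predictor is nearly constant in the tumors that need imputing, under the binary definition of control. If sub-threshold growth makes loss more likely, the bias is upward: +0.4 to +1.0 points at about 11% missing in the scenarios run, and zero if it does not. For scale, the design rate of 91% lies 2.1 points above the 88.9% pass mark at 226 tumors, although that comparison does not measure false-pass risk. At 10% missing the simulated false-pass rate stays near nominal; it rises to 4.4% and 5.8% only at 20% and 30% missing.

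The documents do not support the flat statement that the primary test is biased toward success. That needs growth-related missingness, whose strength they do not give. The figures also ignore correlation between tumors in one patient.

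**What to change.** In Handling of Missing Data, define tumor status and list these further predictors for the FCS logistic model:
- the change of the three-axis sum from its nadir at the last available scan, divided by the month-1 sum (or the month-3 sum where Protocol 8.7 makes that the reference), as a continuous variable. A plain ratio to nadir fails because 8.7.1 records a vanished zone as 0 mm;
- baseline tumor size, as a continuous variable;
- lung progression beyond the index tumor, already assessed at each visit from month 1.

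Keep the list this short. In the 35% v 7% scenario only about 226 × (0.863 − 0.802) ≈ 14 observed failures inform the model.

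Two additions should be avoided. Reason for missing has no value in tumors with an observed outcome, so its coefficient cannot be estimated. A later scan without failure should not by itself set month 12 to controlled. With a nadir of 50, a sum of 65 at month 12 is a failure (+30%), while 55 at month 18 is not (+10%); a rule that can only add successes also pushes toward passing. If month-18 or month-24 status is used, enter it as an auxiliary variable for both control and failure, in tumors not retreated in between.

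The cost is SAP wording and some programming, with no new data. The estimated control rate may fall slightly.

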Galil Medical**CUC13-LNG079-02: Multi-center Study of Metastatic Lung Tumors Targeted by Interventional Cryoablation Evaluation (SOLSTICE)****Statistical Analysis Plan (SAP)****Table of Contents**

Protocol Summary	2
Objective	2
Study Design.....	2
Sample Size Justification.....	2
General Analysis Methods	3
Analysis Populations	3
Efficacy Endpoint Analysis	4
Efficacy Endpoint.....	4
Analysis Methods	4
Safety Endpoint Analysis.....	4
Safety Endpoint	4
Analysis Methods	4
Supportive Endpoint Analyses	5
Tumor control (patient level & weighted average response).....	5
Tumor control (pulmonary metastatic disease).....	5
Tumor control (additional cryoablation).....	5
Technically successful treatment	5
Disease recurrence or progression	5
Intra-procedural data	6
Physical performance and quality of life.....	6
Additional Data Summaries	7
Subject Disposition.....	7
Randomization and Blinding	8
Handling of Missing Data	8
Subset Analyses	8
Poolability Analyses	8
Interim Reporting.....	9
Statistical Software	9
Version, Revision History, and Approvals	10

Current Version	10
Revision History.....	10
Approvals.....	11

Protocol Summary

Objective

The objective of this study is to assess the safety and to demonstrate efficacy of cryoablation in local tumor control for tumors ≤ 3.5 cm in patients with pulmonary metastatic disease.

Study Design

This is a Phase II multicenter, prospective, single arm. Target inclusion for this study is 226 lesions. It is estimated this study will enroll 150 patients in order to achieve the target lesion goal. Patients enrolled will undergo cryoablation of at least 1 metastatic pulmonary tumor via a Galil Medical cryoablation system using Galil Medical cryoablation needles.

Patients will be screened within 8 weeks of the cryoablation procedure. After the cryoablation procedure visit date, protocol directed follow-up visits will consist of within 1 Week of the cryoablation procedure and then 1, 3, 6, 12, 18, and 24 months post cryoablation procedure.

Sample Size Justification

This is a prospective, single-arm study designed to determine the safety and efficacy of Galil Medical's Cryoablation System and needles in cryoablation of metastatic lung tumors.

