The primary efficacy endpoint for the trial is 12-month local control. The papers shown below were used as reference for clinicians who determined a clinically relevant efficacy endpoint performance goal was 84% success at 12-months. This observed cryoablation group's local control rate will be tested against this performance goal.

Paper	Lesions	12-month Local Control Success	Lower 97.5% 1-sided Wilson CI
Okuneiff (2006)	125	91%	0.8469
Rusthoven (2009)	63	100%	0.9425
Baschnagel (2013)	47	97%	0.8757
Ricardi (2012)	77	94%	0.8632
Norihisa (2008)	43	94.50%	0.8337
Yoon (2006)	101	90%	0.8261

This test is accomplished by testing against the following hypotheses:

$$H_0: C_{\text{DEVICE}} \leq 84.0\%$$

$$H_a: C_{\text{DEVICE}} > 84.0\%$$

where C_{DEVICE} is the observed cryoablation local control rate at 12-months.

The null hypothesis will be rejected and the primary efficacy endpoint performance goal will be met if the lower bound of the one-sided 97.5% confidence interval for the 12-month tumor local control rate is greater than 84.0%.

PASS 12 was used to calculate the sample size needed. A sample size of 203 lesions achieves 85% power (and guarantees at least 80% power) to detect a difference ($P_1 - P_0$) of 0.0700 using a one-sided binomial test. The target significance level is 0.0250. The actual significance level achieved by this test is 0.0239. These results assume that the population proportion under the null hypothesis is 0.8400.

Power Analysis of One Proportion

Numeric Results for testing $H_0: P = P_0$ versus $H_1: P > P_0$

Test Statistic: Exact Test

Power	N	Proportion		Target Alpha	Actual Alpha	Beta	Reject H_0 If $R \geq$ This
		Given H_0 (P_0)	Given H_1 (P_1)				
0.8501	203	0.8400	0.9100	0.0250	0.0239	0.1499	181

To account for up-to a 10% 12-month lesion attrition rate, the final sample size has been increased to 226 lesions.

Note that, for the purposes for sample size calculations, the observations are assumed to be independent. However, the primary analyses will account for within subject correlation, as described below.

General Analysis Methods

Data will be analyzed using descriptive statistics. Continuous variables (e.g., age) will be summarized by the number of patients, mean, standard deviation, median, interquartile range, minimum and maximum. Categorical variables (e.g., race) will be summarized by frequencies and percentages of patients in each category. 95% confidence intervals will be calculated as appropriate.

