Analysis Populations

All primary analyses will be performed on all tumors with a Galil Medical Cryoablation System and needles as the intent-to-treat evaluable population. A supplemental per-protocol analysis

will be done for the primary endpoint, removing tumors that 1) did not have a complete treatment; and subjects who 2) did not meet the study criteria but were enrolled; or 3) had a deviation with high likelihood of affecting the study outcome (as determined by a review of all occurring deviations).

The intent-to-treat and per-protocol analyses will be compared for level of agreement. It is expected that the two populations will be similar; however, any substantial differences between the two will be analyzed appropriately to elucidate the cause of these differences. Missing data will be imputed for the primary analysis as outlined in section "Handling of Missing Data" section later in the SAP. Additional sensitivity analyses using alternate missing data imputation will be presented.

Efficacy Endpoint Analysis

Efficacy Endpoint

The primary efficacy endpoint for this study is assessment of cryoablation on local tumor control in patients with pulmonary metastatic disease at 12 months post cryoablation.

Analysis Methods

The primary efficacy endpoint for this study is defined as follows: local tumor control in patients with pulmonary metastatic disease at 12 months post cryoablation. Tumor control will be defined by the criteria defined in Section 9.7 of this protocol.

Patients are allowed up to 6 tumors and the primary efficacy endpoint (tumor control) will be calculated on a per tumor level.

The rate of local tumor control at 12-months will be analyzed using a random effects logistic regression model accounting for within subject correlation to account for multiple tumors per subject. The null hypothesis will be tested comparing the lower bound of the Wald 97.5% one-sided confidence interval for the estimated rate of local tumor control to the performance goal of 84.0%. If the lower bound is greater than 84.0%, the null hypothesis will be rejected and the endpoint will be considered met.

Safety Endpoint Analysis

Safety Endpoint

The safety endpoint for this study is to assess the incidence and severity of cryoablation related adverse events.

Analysis Methods

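### The imputation of missing month-12 status names no patient-level information although the primary model has a patient effect; if run one row per tumour, the standard error is modestly too small

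*SAP*

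**What the plan says.** Under Efficacy Endpoint Analysis, Analysis Methods, the SAP analyses each tumour as a unit, with up to six per patient, in a "random effects logistic regression model accounting for within subject correlation". The lower 97.5% one-sided Wald bound for the control rate is compared with 84%. Sample Size Justification treats tumours as independent for planning but repeats that the primary analysis will allow for correlation. The Revision History drops a special provision for few multi-lesion patients because more than 10 patients had several lesions.

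Under Handling of Missing Data, month-12 evaluations missing from this formal test are multiply imputed: "SAS PROC MI using FCS logistic regression and including tumor status at prior visits". The one exception is that a local failure at month 6 counts as a failure at month 12. Worst-case, best-case and complete-case analyses are planned as sensitivity analyses.

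The SAP does not say whether the imputation data set has one row per tumour or one per patient. It also does not say whether the patient's other tumours enter the model, how many imputations are made, or how they are pooled.

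**The concern.** An imputation model should carry at least the structure of the analysis it feeds. Here the analysis has a patient effect and the imputation, as described, has none. On one row per tumour, two missing tumours of the same patient are drawn independently once their own earlier status is known.

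This has two consequences. The completed data sets show less within-patient correlation than the real data, so the random effects model reports too small a variance. The uncertainty of the imputation model itself is also understated, because its observed tumours are counted as independent.

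The mechanism matters most when whole patients are missing, and much of the missingness should be of that kind. One chest CT per visit covers all index tumours, and death, hospice care, loss to follow-up and withdrawal (Protocol 7.8 and 7.9) remove patients. More than the planned 10% may be missing. Two cryoablation series described in Protocol 3.2 report 1-year survival of 91% and 89.4%; the second required a life expectancy above 1 year, whereas this trial requires more than 3 months (Protocol 6.2.10).

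At stake is the width of the interval that decides whether the performance goal is met.

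**Working it through.** **1. The plan's own design.** Inputs from SAP, Sample Size Justification: "A sample size of 203 lesions achieves 85% power (and guarantees at least 80% power) to detect a difference"; "These results assume that the population proportion under the null hypothesis is 0.8400"; "The target significance level is 0.0250"; "The actual significance level achieved by this test is 0.0239". The alternative is 0.91 and the rejection count 181.
- P(X ≥ 181 | n = 203, p = 0.84) = 0.0239; a cut-off of 180 would give 0.0384, so 181 is right.
- P(X ≥ 181 | n = 203, p = 0.91) = 0.8501.
- "To account for up-to a 10% 12-month lesion attrition rate, the final sample size has been increased to 226 lesions": 203 / 0.9 = 225.6, rounded up to 226.
- "It is estimated this study will enroll 150 patients in order to achieve the target lesion goal" (SAP, Study Design): 226 / 150 = 1.51 tumours per patient.

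All figures reproduce. The planned sample size does not depend on the present point.

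**2. Assumptions not in the documents.** The intra-patient correlation ρ is 0.1, 0.3 or 0.5. The 150 patients have 1, 2, 3, 4, 5 or 6 tumours in numbers 99, 34, 12, 3, 1 and 1, which gives 226 tumours. Whole patients are missing at random, in a share m of 10%, 20% or 30%. The true rate is 0.84.

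**3. Hand check of the mechanism, ignoring prior-visit status.** The sum of squared cluster sizes is 99 + 136 + 108 + 48 + 25 + 36 = 452, and 452 / 226 = 2, so the design effect is 1 + ρ. Let V = 0.84 × 0.16 / 226. With many imputations:
- With a patient effect, total variance = V(1 + ρ) / (1 − m), which is also the true variance.
- With independent draws, within-imputation variance = V[1 + (1 − m)ρ] and between-imputation variance = V[m + m² / (1 − m)]. Their sum is V[1 / (1 − m) + (1 − m)ρ].
- SE ratio = √{[1 + (1 − m)²ρ] / (1 + ρ)}.

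For m = 0.1 and ρ = 0.3: √(1.243 / 1.3) = 0.978. For m = 0.3 and ρ = 0.5: √(1.245 / 1.5) = 0.911.

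**4. Simulation with prior-visit status.** There were 8,000 runs per cell, with 20 imputations, Rubin's rules and a cluster-robust Wald bound on the logit scale. Half of the failures occurred by month 6, month-6 status was known for half of the missing patients, and month-6 failures were carried forward.

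| Missing | ρ | SE ratio, hand check | SE ratio, simulated | Reported SE / true SD, without patient effect | Type I error, without v with patient effect |
|---|---|---|---|---|---|
| 10% | 0.1 | 0.991 | 0.993 | 0.998 | 0.021 v 0.020 |
| 10% | 0.3 | 0.978 | 0.982 | 0.980 | 0.025 v 0.024 |
| 10% | 0.5 | 0.968 | 0.975 | 0.970 | 0.028 v 0.024 |
| 20% | 0.1 | 0.984 | 0.986 | 0.985 | 0.021 v 0.020 |
| 20% | 0.3 | 0.958 | 0.965 | 0.973 | 0.024 v 0.020 |
| 20% | 0.5 | 0.938 | 0.950 | 0.953 | 0.028 v 0.023 |
| 30% | 0.1 | 0.977 | 0.981 | 0.979 | 0.023 v 0.020 |
| 30% | 0.3 | 0.939 | 0.951 | 0.957 | 0.029 v 0.023 |
| 30% | 0.5 | 0.911 | 0.928 | 0.937 | 0.029 v 0.021 |

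The SE ratio is the SE without a patient effect divided by the SE with one. With a patient effect, reported SE / true SD lies between 0.996 and 1.010, so the narrower interval is an error and not a gain in efficiency. The simulated shortfall is smaller than in the hand check because prior-visit status carries part of the correlation. The Monte Carlo SE of the type I error is √(0.025 × 0.975 / 8,000) ≈ 0.002.

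**5. Check with a random-intercept logistic model, the kind the SAP names.** This was smaller: 480 runs, 5 imputations and no prior-visit status. The patient-effect imputation used the true patient SD.

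| True patient SD | Missing | SE ratio | Estimated patient SD, with → without patient effect |
|---|---|---|---|
| 1.5 | 10% | 0.986 | 1.47 → 1.37 |
| 1.5 | 30% | 0.969 | 1.43 → 1.08 |
| 2.5 | 10% | 0.980 | 2.44 → 2.21 |
| 2.5 | 30% | 0.959 | 2.44 → 1.74 |

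**6. Effect on the bound, approximated on the probability scale.** At 10% missing and ρ = 0.3, the lower bound moves by 1.96 × (0.0289 − 0.0284) = 0.0010, or 0.10 percentage points. At 30% missing and ρ = 0.5 it moves by 1.96 × (0.0343 − 0.0319) = 0.0047, or 0.47 points. One tumour in 226 is 0.44 points.

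**The case against.** A reader might infer that the SAP prescribes imputation tumour by tumour and treats a patient's tumours as independent. It does not say so. It names one predictor without calling the list complete and gives no layout. One row per patient, or the status of the other tumours as predictors, would fit the same words. This objection stands, which is why the point is conditional. One row per tumour is still the natural reading, since endpoint and analysis are per tumour. With 1.51 tumours per patient, a layout with six tumour columns would be mostly empty and would itself need describing.

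Even on tumour rows, the draws are independent only given earlier status, and month-6 failures are not drawn. That exception is worded for subjects, which read literally would add agreement within patients. This too stands. The main simulation used prior-visit status and carried failures forward tumour by tumour, and a shortfall remained.

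Missingness by whole patient is an assumption. Protocol 7.8 restarts follow-up for a retreated lesion alone, and Protocol 8.7 assesses each ablation zone separately and foresees indeterminate measurements. Some tumours may therefore be missing singly, which weakens the effect.

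The complete-case analysis avoids this mechanism, but it is a sensitivity analysis and not the formal test.

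**Conclusion.** The point holds as a gap in specification with a modest consequence. The primary model has a patient effect, and the imputation that feeds it names no patient-level information. Run on one row per tumour, it gives a standard error that is too small relative to imputation with a patient effect: by about 1% to 3% at 10% missing, 1% to 5% at 20% and 2% to 7% at 30%, for correlations of 0.1 to 0.5.

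These sizes rest on the assumed correlation, cluster sizes, missingness by whole patient at random, and share of failures seen by month 6. At a correlation of 0.1 and 10% missing, the shortfall is negligible.

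A reader might go further and conclude that the primary test is anti-conservative to a degree that matters. The figures do not support that. One-sided type I error lies between about 0.02 and 0.03 in every setting, and the lower bound moves by about one tumour's worth at most. Severity is minor: a cheap improvement, not a threat to the conclusion.

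**What to change.** In Handling of Missing Data, state the layout of the imputation data set. Impute month-12 status by multilevel logistic regression with a patient random intercept shared by all tumours of that patient, to match the analysis model. Keep tumour status at prior visits, and add the number of index tumours and the status of the patient's other tumours as predictors. These predictors alone are only a partial fix: in simulation, the failure status of the other tumours recovered only part of the shortfall. The shared patient effect is the part that matters. State the number of imputations and the pooling rule as well. Keep the complete-case random effects analysis as a check.

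The cost is SAP wording, some programming outside PROC MI, and a slightly wider interval. The planned number of tumours does not change.
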